Improved ORR of 42.5% versus 28.7% and CBR of 79.9% vs 73.1% were for the ribociclib plus letrozole arm relative to placebo plus letrozole arm. The median time to response was not achieved in either treatment arm. Median duration of response is 26.7 months (95% CI: 24.0, NE) with ribociclib + letrozole versus 18.6 months (95% CI: 14.8, 23.1) with placebo + letrozole.

The ORR (54.5% vs. 38.8%) and CBR (80.2% vs. 71.8%) in the subgroup of patients with measurable disease at baseline were consistent with the primary analysis results.

1.10 FDA Approval

Ribociclib was approved by the FDA on March 13, 2017 for use in combination with an AI for post-menopausal, hormone receptor positive, Her-2/neu negative recurrent breast cancer, based on findings from the phase III MONALEESA-2 trial. In that study, the combination of ribociclib and letrozole reduced the risk of progression or death by 44% compared with letrozole plus placebo in the first-line setting for HR+/HER2- advanced breast cancer (HR, 0.556; 95% CI, 0.43-0.72; P <.0001).

1.11 Study Agent

Ribociclib (formerly LEE011) is an orally bioavailable, highly selective small molecule inhibitor of cyclin-dependent kinases 4 and 6 (CDK4/6). Ribociclib has been approved by the United States Food and Drug Administration (U.S. FDA) and the European Commission as an initial endocrine-based therapy for the treatment of postmenopausal women with hormone receptor (HR)-positive, human epidermal growth factor receptor 2 (HER2)-negative advanced or metastatic breast cancer in combination with an aromatase inhibitor based on a randomized, double-blind, placebo-controlled, international clinical trial (MONALEESA-2). Additional marketing authorizations are under review by health authorities. Additional phase III clinical trials for the treatment of hormone receptor positive (HR+) breast cancer patients, as well as several other phase I or II clinical studies are being conducted.

1.12 Post-marketing experience

Kisqali® (Ribociclib) in combination with an aromatase inhibitor as initial endocrine-based therapy for the treatment of postmenopausal women with hormone receptor (HR)-positive, human epidermal growth factor receptor 2 (HER2)-negative advanced or metastatic breast cancer was approved by the FDA on 13 March 2017, and by the European Commission on 22-Aug-2017. Other health authority reviews are currently ongoing. Additional marketing approvals are expected on an ongoing basis.

Kisqali® is commercially available as 200 mg film coated tablets in 3 presentations – 63 tablets, 42 tablets and 21 tablets. On 04-May-2017 the FDA also approved the Kisqali Femara Co-pack for the same indication. The Co-pack contains both Kisqali and 26 day supply of Femara (letrozole) tablets.

1.13 Other Agent(s)

Letrozole is a highly potent, orally active non-steroidal competitive inhibitor of the aromatase enzyme system. It effectively inhibits the conversion of androgens to estrogens both in vitro and in vivo. It is indicated both as first-line treatment of postmenopausal women with hormone receptor positive or hormone receptor unknown locally advanced or metastatic

breast cancer as well as for the treatment of advanced breast cancer in postmenopausal women with disease progression following antiestrogen therapy.

Letrozole was initially studied at doses of 0.1mg to 5.0mg daily in six non-comparative Phase I/II trials in 181 postmenopausal estrogen/progesterone receptor positive or unknown advanced breast cancer patients previously treated with at least antiestrogen therapy. Patients had received other hormonal therapies and also may have received cytotoxic therapy. Eight (20%) of forty patients treated with letrozole 2.5mg daily in Phase I/II trials achieved objective tumor response (complete or partial response).

A randomized, double-blinded, multinational trial compared Letrozole 2.5mg with tamoxifen 20mg in 916 postmenopausal patients with locally advanced (Stage IIIB or loco-regional recurrence not amenable to treatment with surgery or radiation) or metastatic breast cancer. Time to progression (TTP) was the primary endpoint of the trial. Letrozole was superior to tamoxifen in TTP and rate of objective tumor response.

1.14 Rationale

Based on encouraging results in women with advanced hormone-receptor-positive breast cancer, a clinical trial for women with recurrent low-grade serous carcinoma is warranted. Furthermore, such a trial would have great appeal to women with recurrent low-grade serous carcinoma, a cohort with limited therapeutic options. Although low-grade serous carcinoma is a rather uncommon histologic subtype, prolonged overall survival results in a relatively high prevalence.

1.15 Gender and Ethnicity

This study will be open to women, including members of any minority groups and their subpopulations.

2.0 OBJECTIVES

2.1 Primary Objective

1. To determine the proportion of patients who have objective tumor response (complete or partial) within one year from start of study treatment as assessed by RECIST 1.1 in patients with recurrent low-grade serous carcinoma of the ovary, fallopian tube or peritoneum treated with the combination of ribociclib + letrozole.

2.2 Secondary Objectives

- To examine the proportion of patients who have clinical benefit (complete response [CR], partial response [PR], or stable disease [SD]) in patient with recurrent low-grade serous carcinoma of the ovary, fallopian tube or peritoneum treated with the combination of ribociclib + letrozole.
- 2. To estimate the nature, frequency, and maximum degree of toxicity associated with this combination using CTCAE v5.
- 3. To estimate the progression-free survival of women receiving the combination of ribociclib + letrozole.
- 4. To estimate the overall survival of women receiving the combination of ribociclib + letrozole.

2.3 Exploratory Objectives

- 1. To determine the expression of Rb, estrogen receptor (ER), progesterone receptor (PR), and proliferative index (ki-67) and their correlation with response and clinical benefit.
- 2. To determine genomic signatures associated with response and clinical benefit of the combination of ribociclib + letrozole. (Note: for the exploratory objectives, no additional tissue biopsy will be required. We will test the recurrent tumor if available. If not we will test the primary tumor).

2.4 Endpoints

- 2.4.1 Primary endpoints
- 1. Objective Response rate as determined by RECIST 1.1.
 - 2.4.2 Secondary endpoints
- 1. Clinical benefit (CR, PR, SD) rate.
- 2. Toxicity using CTCAE v5.0.
- 3. Progression-free survival

4. Overall survival

2.4.3 Exploratory endpoints

- 1. Expression of ER, PR, and ki-67 and their correlation with response and clinical benefit.
- 2. Genomic signatures and their correlation with response and clinical benefit.

3.0 PATIENT SELECTION

3.1 Inclusion Criteria

- 1. Patient has signed the Informed Consent (ICF) prior to any screening procedures being performed and is able to comply with protocol requirements.
- 2. Age \geq 18 years at time of study entry.
- 3. Willingness and ability to comply with study and follow-up procedures.
- 4. Histological confirmation of diagnosis of low-grade serous carcinoma of ovary, fallopian tube or peritoneum; Original diagnosis of de novo low-grade serous carcinoma or Original diagnosis of serous borderline tumor with subsequent diagnosis of low-grade serous carcinoma
 - In order to prevent inclusion of patients with high-grade serous carcinoma, diagnosis of low-grade serous carcinoma will be verified as part of a screening review by a gynecologic pathologist. Tissue for confirmation can be from primary tumor or recurrence.
- 5. Patient must have recurrent, measurable disease by RECIST v1.1.
- 6. There are no restrictions on number of prior therapies.
- 7. Patient cannot have previously received a prior cyclin dependent kinase inhibitor (CDKi). Patients who were treated with letrozole or another aromatase inhibitor for other indications must have not taken the drug for 6 months prior to initiating letrozole for this trial and may not have progressed on treatment.
- 8. Patients must not have remaining ovarian function to be included. In women who have at least one retained ovary, menopause must be confirmed with laboratory confirmation. Women who have ovarian function are eligible but must be placed on hormonal suppression. Menopause must be confirmed with laboratory confirmation, to include an estradiol level as this is assessed within 8 weeks of patient having been on tamoxifen.
- 9. Eastern Cooperative Oncology Group (ECOG) performance status (PS) 0-2
- 10. Resolution of all acute toxic effects of prior therapy or surgical procedures to National Cancer Institute (NCI) CTCAE Grade ≤ 1. Patients with grade 1 taxane-induced neuropathy, any grade alopecia, amenorrhea, or other toxicities not considered a safety risk for the patient as per investigator's discretion are eligible.

- 11. Patient has adequate bone marrow and organ function as defined by the following laboratory values at screening:
 - a. Absolute neutrophil count ≥1.5 × 10⁹/L
 - b. Platelets $\geq 100 \times 10^9/L$
 - c. Hemoglobin ≥9.0 g/dL
 - d. Potassium, total calcium (corrected for serum albumin), magnesium, sodium and phosphorus within normal limits for the institution or corrected to within normal limits with supplements before first dose of study medication
 - e. INR ≤1.5 (unless patient is receiving permitted anticoagulants and the INR is within the therapeutic range of intended use for that anticoagulant within 7 days prior to the first dose of study drug).
 - f. Serum creatinine <1.5 mg/dL or creatinine clearance ≥50 mL/min
 - g. In the absence of liver metastases, alanine aminotransferase (ALT) and aspartate aminotransferase (AST) < $2.5 \times ULN$. If the patient has liver metastases, ALT and AST < $5 \times ULN$
 - h. Total bilirubin < ULN; or total bilirubin \le 3.0 x ULN or direct bilirubin \le 1.5 x ULN in patients with well-documented Gilbert's Syndrome.
- 12. Patient with available standard 12-lead ECG with the following parameters at screening:
 - a. QTcF interval at screening <450msec (using Fridericia's correction)
 - b. Resting heart rate 50-90bpm
- 13. Must be able to swallow ribociclib and letrozole capsules/tablets.
- 14. Patients receiving tamoxifen or toremifene must have washout period of 5 half-lives prior to randomization.

3.2 Exclusion Criteria

Patients eligible for this study must not meet any of the following criteria:

- 1. Patient has a known hypersensitivity to any of the excipients of ribociclib or letrozole.
- 2. Patient has a concurrent malignancy or malignancy within 3 years prior to starting study drug, with the exception of adequately treated, basal or squamous cell carcinoma, non-melanomatous skin cancer or curatively resected cervical cancer. Patients with known brain metastases are excluded.
- 3. Patients with central nervous system (CNS) involvement unless they meet ALL of the following criteria:
 - a. At least 4 weeks from prior therapy completion (including radiation and/or surgery) to starting the study treatment
 - b. Clinically stable CNS tumor at the time of screening and not receiving steroids and/or enzyme inducing anti-epileptic medications for brain metastases.
- 4. Patient has impairment of gastrointestinal (GI) function or GI disease that may significantly alter the absorption of the study drugs (e.g., ulcerative diseases, uncontrolled nausea, vomiting, diarrhea, malabsorption syndrome, or small bowel resection).

- 5. Patient has a known history of HIV infection (testing not mandatory).
- 6. Patient has any other concurrent severe and/or uncontrolled medical condition that would, in the investigator's judgment, cause unacceptable safety risks, contraindicate patient participation in the clinical study or compromise compliance with the protocol (e.g. chronic pancreatitis, chronic active hepatitis, active untreated or uncontrolled fungal, bacterial or viral infections, etc.).
- 7. Clinically significant, uncontrolled heart disease and/or cardiac repolarization abnormalities, including any of the following:
 - a. History of acute coronary syndromes (including myocardial infarction, unstable angina, coronary artery bypass grafting, coronary angioplasty, or stenting) or symptomatic pericarditis within 6 months prior to screening
 - b. History of documented congestive heart failure (New York Heart Association functional classification III-IV)
 - c. Documented cardiomyopathy
 - d. Left Ventricular Ejection Fraction (LVEF) <50% as determined by Multiple Gated acquisition (MUGA) scan or echocardiogram (ECHO)
 - e. Clinically significant cardiac arrhythmias (e.g. ventricular tachycardia), complete left bundle branch block, high-grade AV block (e.g. bifascicular block, Mobitz type II and third-degree AV block)
 - f. Long QT syndrome or family history of idiopathic sudden death or congenital long QT syndrome, or any of the following:
 - i. Risk factors for Torsades de Pointe (TdP) including uncorrected hypocalcemia, hypokalemia or hypomagnesemia, history of cardiac failure, or history of clinically significant/symptomatic bradycardia.
 - ii. Concomitant use of medication(s) with a known risk to prolong the QT interval and/or known to cause Torsades de Pointe that cannot be discontinued (within 5 half-lives or 7 days prior to starting study drug) or replaced by safe alternative medication
 - iii. Inability to determine the QT interval on screening (QTcF, using Fridericia's correction)
 - iv. Systolic blood pressure (SBP) >160 mmHg or <90 mmHg at screening
- 8. Patient is currently receiving any of the following medications and cannot be discontinued 7 days prior to starting study drug (see Table 1 for details):
 - a. Known strong inducers or inhibitors of CYP3A4/5, including grapefruit, grapefruit hybrids, pummelos, star-fruit, and Seville oranges
 - b. That have a narrow therapeutic window and are predominantly metabolized through CYP3A4/5
 - c. Herbal preparations/medications, dietary supplements.
- 9. Participation in other studies involving investigational drug(s) within 30 days prior to randomization or within 5 half-lives of the investigational product (whichever is longer) or

- participation in any other type of medical research judged not to be scientifically or medically compatible with this study. If the patient is enrolled or planned to be enrolled in another study that does not involve an investigational drug, the agreement of the Novartis study medical lead is required to establish eligibility.
- 10. Patient is currently receiving warfarin or other coumadin-derived anticoagulant for treatment, prophylaxis or otherwise. Therapy with heparin, low molecular weight heparin (LMWH) or fondaparinux is allowed. Direct-Acting Oral Anticoagulants (DOACs) are permitted.
- 11. Patient is currently receiving or has received systemic corticosteroids ≤2 weeks prior to starting study drug, or who have not fully recovered from side effects of such treatment. The following uses of corticosteroids are permitted: a short duration (< 5 days) of systemic corticosteroids; any duration of topical applications (e.g., for rash), inhaled sprays (e.g., for obstructive airways diseases), eye drops or local injections (e.g., intra-articular).
- 12. Patient who has received radiotherapy ≤4 weeks or limited field radiation for palliation ≤2 weeks prior to starting study drug, and who has not recovered to grade 1 or better from related side effects of such therapy (exceptions include alopecia) and/or in whom ≥25% of the bone marrow (Ellis, 1961) was irradiated.
- 13. Patient has had major surgery within 14 days prior to starting study drug or has not recovered from major side effects (tumor biopsy is not considered as major surgery).
- 14. Patient with a Child-Pugh score B or C.
- 15. Patients who are pregnant or breastfeeding
- 16. Women of child-bearing potential, defined as all women physiologically capable of becoming pregnant, unless they are using highly effective methods of contraception throughout the study and for 3 weeks after study drug discontinuation. Highly effective contraception methods include:
 - Total abstinence when this is in line with the preferred and usual lifestyle of the patient. Periodic abstinence (e.g., calendar, ovulation, symptothermal, post-ovulation methods) and withdrawal are not acceptable methods of contraception
 - Female sterilization (have had surgical bilateral oophorectomy with or without
 hysterectomy), total hysterectomy, or tubal ligation at least six weeks before taking
 study treatment. In case of oophorectomy alone, only when the reproductive status
 of the woman has been confirmed by follow up hormone level assessment

Women are considered post-menopausal and not of child bearing potential if they have had 12 months of natural (spontaneous) amenorrhea with an appropriate clinical profile (e.g. age appropriate, history of vasomotor symptoms) or have had surgical bilateral oophorectomy (with or without hysterectomy) or tubal ligation at least six weeks ago. In the case of oophorectomy alone, only when the reproductive status of the woman has been confirmed by follow up hormone level assessment is she considered not of child bearing potential.

- 17. Current use of food or drugs known to be potent CYP3A4 inhibitors, drugs known to be potent CYP3A4 inducers, and drugs that are known to prolong the QT interval (see Appendix C for Prohibited Concomittant Medications).
- 18. Patients whose tumors contain both low-grade serous carcinoma (LGSC) and high-grade serous carcinoma (HGSC).
- 19. Patients with history of haemopoietic stem cell or bone marrow transplant.

4.0 STUDY DESIGN

This is an open-label, multi-institution, phase II trial. Eligible subjects with recurrent low-grade serous carcinoma who sign informed consent will receive the combination of letrozole and Ribociclib until disease progression or until they experience significant adverse events.

Table 1. Dose and Treatment Schedule			
Agent	Dose	Route	Schedule
Ribociblib	600 mg	Capsules/tablets for oral use	Daily for 21 days then 7 days off
Letrozole	2.5 mg	Capsules for oral use	Daily
**Doses as appropriate for assigned dose level.			

- Letrozole will be administered at a dose of 2.5 mg by mouth daily with continuous treatment until progression or unacceptable toxicity. The dose of letrozole will not be modified.
- Ribociclib will be administered at a dose of 600 mg by mouth daily for 21 days followed by 7 days off treatment. Treatment will be until progression or unacceptable toxicity.

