4.2 TREATMENT PLAN: Letrozole

Letrozole is formulated as tablets of 2.5 mg and supplied in bottles. The dose of letrozole is one 2.5 mg tablet administered orally once daily. The oral single dose of ribociblib should be taken together with the daily dose of letrozole 2.5 mg as per schedule below.

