4.5.2.4 Guidelines for Administration

Letrozole tablets are taken orally without regard to meals.

Recommended dose: 2.5.mg once daily.

Patients with cirrhosis or severe hepatic impairment: 2.5 mg every other day

4.5.2.5 Supplier: Letrozole will be supplied by Novartis or its designee. Please refer to the Regulatory Manual for drug ordering instructions and forms.

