4.7.2 Letrozole - Dose Modification Guidelines

Toxicity Site	Observation	Management
Bone Effects	Use of Letrozole may cause decreases in bone mineral density (BMD)	Consideration should be given to monitoring BMD
Grade 3-4 hypercholesterolemia	Hypercholesterolemia was reported in 52.3% of letrozole patients and 28.6% of tamoxifen patients.	Consideration should be given to monitoring serum cholesterol.
Subjects with cirrhosis and severe hepatic impairment		Reduce dose to 2.5mg every other day

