APPENDIX D- PATIENT PILL CALENDAR:

Patient Name:	Date of first dose on calendar:
Patient Study ID:	Cycle #:

- Complete one form for each cycle of treatment
- You will take Ribociclib once a day for 21 days followed by 7 days off. You will take Letrozole once a day every day.
- Please bring this form and your bottles of Letrozole and Ribociclib each time you return for an appointment

	1 appointm			, 		
Day	Date	Time of Ribociclib	Dose	Time of	Dose	
		Dose	taken	Letrozole Dose	taken	Comments
1						
2						
3						
4						
5						
6						
7						
8						
9						
10						
11						
12						
13						
14						
15						
16						
17						
18						
19						
20						
21						
22						
23						
24						
25						
26						
27						
28						

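### Section 4.0 rules out any letrozole dose change, but Sections 4.5.2.4 and 4.7.2 halve it for cirrhosis or severe hepatic impairment, with an ambiguous trigger

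*Combined protocol and SAP*

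**What the plan says.** Five places in the combined protocol and SAP instruct on the letrozole dose, and one exclusion criterion decides who can meet the hepatic rule.

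- Section 4.0, after setting 2.5 mg daily as continuous treatment: "The dose of letrozole will not be modified". There is no exception and no pointer to another section.
- Section 4.2: "The dose of letrozole is one 2.5 mg tablet administered orally once daily".
- Section 4.5.2.4, under administration: "Patients with cirrhosis or severe hepatic impairment: 2.5 mg every other day".
- Section 4.7.2, headed "Letrozole - Dose Modification Guidelines": for "Subjects with cirrhosis and severe hepatic impairment" the action is "Reduce dose to 2.5mg every other day". The other two rows of that table (bone effects, hypercholesterolemia) only suggest monitoring, so the hepatic row is the only one that changes the dose.
- Appendix D, the patient's own calendar: "You will take Letrozole once a day every day".
- Section 3.2, Exclusion 14: "Patient with a Child-Pugh score B or C". No criterion excludes cirrhosis by name.

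**The concern.** A flat prohibition and two reduction rules stand in the same protocol, and nothing ranks them. For a patient who meets the hepatic trigger, every-other-day letrozole is directed by one section and is a departure from another.

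Two things are at stake. The first is patient safety: the site and the patient can be working from different instructions, since the pill calendar carries only the daily one. The second is the definition of the regimen. Compliance is checked at each visit (Section 4.5.1.4), and non-compliance with the protocol is a listed reason to end treatment (Section 9.1). The same conduct could therefore be recorded as adherence at one center and as a deviation at another. The synopsis expects 25 centers, so uneven handling is foreseeable.

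**Working it through.** No power, error rate or sample size enters here. The check is a comparison of text plus one line of arithmetic.

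**1. Does the hepatic rule really modify the dose?** One could say that each tablet is still 2.5 mg and only the interval changes. The protocol closes that route itself: Section 4.7.2 sits under a dose-modification heading and its action is worded as a dose reduction. The conflict with Section 4.0 is therefore literal.

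**2. Can an eligible patient meet the trigger at entry?** Exclusion 14 removes Child-Pugh B and C, which leaves Child-Pugh A. Inclusion 11 (Section 3.1) further requires:
- total bilirubin below the upper limit of normal (ULN), with an allowance for Gilbert's syndrome;
- ALT and AST below 2.5 x ULN, or below 5 x ULN with liver metastases;
- INR of at most 1.5, with an allowance for permitted anticoagulants.

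A patient with compensated cirrhosis and near-normal liver tests can pass all of these, unless the investigator excludes her by judgment under Exclusion 6.

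**3. What does each section tell that patient (Child-Pugh A cirrhosis, no severe impairment)?**

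| Place | Instruction |
|---|---|
| 4.0 | daily, no modification |
| 4.2 | daily |
| 4.5.2.4 | every other day (cirrhosis alone meets the or) |
| 4.7.2, and read as requiring both conditions | no reduction, so daily |
| 4.7.2, and read as listing two groups | every other day |
| Appendix D | daily |

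There are two regimens. Section 4.7.2 falls on one side or the other depending on how its row label is read.

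**4. Size of the difference, per 28-day cycle.**
- Daily: 28 tablets x 2.5 mg = 70 mg.
- Every other day: 28 / 2 = 14 tablets; 14 x 2.5 mg = 35 mg.
- Ratio: 70 / 35 = 2.

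**5. Can the question arise on treatment?** The hepatic tables in Section 4.7.1.2 direct action on ribociclib and give no letrozole instruction. The follow-up text there calls for immediate discontinuation of study drug when combined transaminase and bilirubin criteria are met without cholestasis, but does not say whether study drug includes letrozole. Under Section 9.1.3 a patient is off study therapy on progression, death, start of non-protocol therapy, or when all study therapy has stopped. Stopping ribociclib alone therefore does not by itself end letrozole. If cirrhosis or severe hepatic impairment is then found, Sections 4.0, 4.5.2.4 and 4.7.2 again apply without a stated order.

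**The case against.** The strongest reply is that a sensible reader can rank the sections. Section 4.0 gives the general regimen, Section 4.7.2 is the specific rule, and Section 4.5.2.1 refers to the package insert. That is a reasonable way to read a protocol. But the document never says that the specific rule governs, and the sentence in Section 4.0 is unqualified, so a clarification is still due.

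The second reply is that eligibility leaves almost nobody affected at entry. This stands as a limit on size: Exclusion 14, the laboratory limits and Exclusion 6 together narrow the group to compensated cirrhosis, and nothing in the documents suggests that it is common in this population. It does not remove the conflict. If the criteria did make the rule irrelevant, two sections would carry a dosing rule with no one at entry to apply it to.

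The third reply is that on-treatment liver toxicity is already managed, since Section 9.1 allows treatment to end for unacceptable adverse events or on investigator judgment. That is true, but these provisions do not say what letrozole dose applies to a patient who continues.

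Some stronger readings are tempting and are not supported:

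- *That the or/and difference is a second proven contradiction.* The row label in Section 4.7.2 can naturally be read as naming two groups, which would match Section 4.5.2.4. The wording is ambiguous, and the conflict with Section 4.0 remains on either reading.
- *That a patient faces three different instructions.* Only two regimens exist, as the table above shows.
- *That any hepatic impairment triggers the rule.* Both sections say severe.
- *That the phase III discontinuation figures in the background (ALT increase 4.5%, AST increase 2.7%) estimate how many patients are affected.* Those are transaminase rises that led to stopping ribociclib in breast cancer patients. No transaminase or bilirubin grade triggers a letrozole reduction anywhere in this protocol, so the figures do not count patients with cirrhosis or severe hepatic impairment.

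**Conclusion.** The point holds as an internal contradiction on dosing with an ambiguous trigger. An unqualified statement in Section 4.0, echoed by Section 4.2 and Appendix D, is incompatible with Sections 4.5.2.4 and 4.7.2 for any patient who meets the hepatic condition.

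For such a patient the planned letrozole exposure differs by a factor of two. How many there will be cannot be derived from the documents. Given the eligibility criteria the number is likely small, and most enrolled patients are unaffected. The conclusion assumes only that Child-Pugh A cirrhosis is not excluded by some criterion outside the text, and that Section 4.0 means what it says.

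The sample size, two-stage decision rules and error rates do not change. The reasons to act are patient safety and a clearly defined regimen, at trivial cost.

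**What to change.** Reconcile Sections 4.0, 4.2, 4.5.2.4, 4.7.2 and Appendix D with each other and with Exclusion 14, so that the protocol contains:

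1. one statement on whether the letrozole dose may be modified, with Section 4.0 worded to agree with it;
2. one unambiguous condition, identical wherever it appears, that settles whether either condition suffices or both are needed;
3. a statement of whether the condition applies at entry (in particular to Child-Pugh A cirrhosis), on treatment, or both;
4. patient instructions in Appendix D consistent with whatever is decided.

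It would also help to say in Section 4.7.1.2 whether study drug includes letrozole. Which rule is clinically right is for the sponsor to decide and is not judged here.

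The cost is protocol wording and a revised pill calendar if needed. No change to the sample size, data collection or analysis follows from it.
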